2.6.5.1 Bupropion Pharmacokinetic Sessions

Subjects will be studied in the Clinical Research Unit at Washington University-Barnes Jewish Hospital, and remain in the Unit for approximately 24 hours. Subjects are instructed to 1) have nothing to eat or drink after midnight before the study session and 2) abstain from alcohol for 24 hours before each study period and until the last sample is collected. Because food increases plasma C_{max} and AUC of bupropion extended-release tablets by 11 and 17%, respectively (although changes were not statistically significant¹⁸), subjects will nonetheless be studied after an overnight fast to minimize potential variability. They will take their study drug with 240ml of water, receive a standard meal 4 hours after bupropion dosing, and have free access to food and water thereafter. An intravenous catheter will be placed by CRU CONFIDENTIAL: This document is the intellectual property of [name], PhD. Acceptance of this document constitutes the agreement by the recipient that no unpublished information contained herein will be published or disclosed without prior written approval.

nursing staff in an arm vein for blood sampling (5cc, EDTA) immediately before and 1, 1.5, 2, 3, 4, 5, 6, 7, 8, 10, 12, 16, 20 and 24 hr after dosing (15 samples, 75 cc per session, 300 cc over the entire study), and samples centrifuged to obtain plasma. Urine will be collected for 24 hr, kept refrigerated, the volume measured, and aliquots frozen. Samples will be stored at -80°C in the PIs lab. At the end of the 24 study, the intravenous catheter is removed, and subjects leave the research unit. Plasma and urine concentrations of bupropion, hydroxybupropion, erythrohydrobupropion, and threohydrobupropion will be determined using a chiral LC/MS/MS assay.

2.6.5.2 Objective Depression and Side Effects Assessment Sessions

Subjects will visit the medical center twice during each 6-week drug crossover (every 3 weeks). The main outcome measurement for depression will be the Montgomery-Asberg Depression Rating Scale (MADRS).⁴⁴ This is a 10-item checklist, where each item is rated on a scale from 0-6 with anchors at 2-point intervals. It takes about 15 min to administer. A MADRS score of ≤15 at baseline will establish study eligibility. The MADRS was designed to assess treatment-sensitive changes in MDD, and can be used by both psychiatrists and non-psychiatrist raters. A structured interview will also be used, which provides high inter-rater reliability to maximize reliability.⁴⁵ Side effects will be assessed with the self-report Antidepressant Side-Effect Checklist (ASEC).⁴⁶ This well-validated scale has the advantage of being measurable via self-report (versus interview) and can be used in both in-person and EMA assessments.

MADRS and ASEC are the standard clinical methods for depression care (and also research instruments) and will be the clinical metrics to determine if patients have a change in clinical response to bupropion, and if patients should be withdrawn for therapeutic reasons.

2.6.5.3 Smart phone-based Assessments

Standard clinical measures of depressive symptoms are sufficient for detecting relapse, but may be insufficiently sensitive for more subtle changes caused by nonequivalent medication versions. Measuring patients' perspectives on complex, subjective, and often transient events such as symptoms or side effects is a methodological challenge, given both insight and memory biases that affect standard retrospective questionnaires.^{47,48}

Therefore, to gather more frequent and potentially more precise information, daily symptoms and side effects will be assessed via a validated smart phone-based program. This approach (Ecological Momentary Assessments, EMA) is currently in use with other Washington University in St. Louis IRB-approved protocols. Specific procedures include:

- In-person demonstration of the smart phone application with a practice phone at the start of the study.
- Phones will be provided by the study team, and run only the EMA program (i.e., no other applications or calls).
- Participants receive a daily trigger for an assessment, with reminder cues until it is completed.
- The daily assessment (approximately 20 items) will measure: (a) depressive symptoms, using 8 items from the MADRS (excluding the suicide item and the depression observational item), (b) 6 most common self-reported side effects of bupropion, as assessed in the Antidepressant Side-Effect Checklist: dry mouth, insomnia, headache, nausea, agitation and sweating, and (c) a short list (no more than 6) symptoms reported by patients who have reported problems with switching between forms of bupropion.
- Data are automatically uploaded to the University server. They will be reviewed approximately weekly.

Smart phone-based assessments are for research only, and will not be used to determine if patients have a change in clinical response to bupropion, or if subjects should be withdrawn for therapeutic reasons. This will be made clear to subjects.

2.6.6 Post-Study Period

After the fourth 6-week drug session and at the last study clinic visit, subjects will be returned to their original bupropion product, resupplied with their own medication to take, and thanked and provided positive feedback for their participation.

2.6.7 Study Drug and Doses

Four study drugs will be evaluated during the randomization period (no IND is needed):

- 1) Wellbutrin XL® 300mg (Valeant Pharmaceuticals, NDC 64455-731, initially developed by GSK)
- 2) generic bupropion XL 300mg (Mylan Pharmaceuticals, NDC 00378-2009, ANDA 090942)
- 3) generic bupropion XL 300mg (Anchen/Par Pharmaceuticals, NDC 10370-102, ANDA 077284)
- 4) generic bupropion XL 300mg (Watson Labs, NDC 00591-3332, ANDA 077715)

A single lot number of each drug product will be used throughout the study, when available. Lot numbers and expiration dates will be recorded. Drugs will be stored at room temperature (59-77 °F, 15-25 °C) away from light and moisture, or as otherwise specified by the manufacturers. All medications will be secured and maintained by Barnes Jewish Hospital Investigational Pharmacy. Drug supply, dispensing, and accountability logs will be maintained.

Each lot number of each drug product will be characterized with respect to identity, content, and purity. Each lot number of each drug product will undergo appropriate dissolution testing. Bupropion tablets will be over-encapsulated with the same opaque capsule to ensure full double-blinding. Over-encapsulated bupropion tablets will also undergo dissolution testing.

If the drug lot number expires prior to the inclusion and completion of all subjects in the study, the drug remaining will be re-characterized with respect to identity, content, and purity, and undergo appropriate dissolution testing. If equivalence to the pre-study identity, content, purity, and dissolution is established (90-110%), in order to ensure that the product has the same quality, then application will be made to FDA for approval to use after the expiration date and extend the expiration date by 1 year.

2.6.8 Genotyping

Genotyping will be performed by PCR to determine relevant CYP2B6 SNPs. Additional genotyping may be performed to evaluate effects of genetic variability in relevant pathways of bupropion disposition. For example, if identities of the human enzymes responsible for bupropion reduction are published during this investigation, and clinically relevant mutants are identified, then additional SNPs may be evaluated.

2.7 Observations and Measurements

2.7.1 Primary Assessments

The primary outcome measure will be C_{max} and AUC_{0-24} for racemic bupropion, hydroxybupropion, erythrohydrobupropion and threohydrobupropion.

Additional pharmacokinetic/bioequivalence endpoints:

- 1. Plasma C_{max} and AUC₀₋₂₄ for R- and S- bupropion
- 2. Plasma C_{min}, C_{av}, C_{trough}, CL/F, %PTF, and swing for RS-, R- and S-bupropion
- 3. Plasma AUC_{0-t} for RS-, R- and S-bupropion
- 4. Plasma C_{max}, AUC₀₋₂₄, C_{min}, C_{av}, C_{trough} %PTF, CL_f and swing for hydroxybupropion, erythrohydrobupropion, and threohydrobupropion; racemate and their individual isomers (enantiomers/diastereomers)
- 5. Plasma AUC_{0,24} hydroxybupropion/bupropion for racemate and individual enantiomers
- 6. Formation clearance of hydroxybupropion, erythrohydrobupropion, threohydrobupropion, erythrohydrobupropion glucuronide, threohydrobupropion glucuronide: racemate and individual isomers

Secondary Endpoints:

- 7. Relapse of MDD
- 8. Change in symptoms of depression
- 9. Change in side effects of medication

2.7.2 Pharmacokinetic Calculations

Pharmacokinetic parameters will be determined essentially per FDA Guidance. ¹⁰ The primary metrics will be 1) Peak drug exposure, assessed from maximum plasma drug concentration (C_{max}) obtained directly from the data without interpolation; and 2) Total exposure, assessed as the area under the plasma concentration-time curve from time zero to time tau over the dosing interval at steady state (AUC_{0-tau}), analyzed using non-compartmental methods, where tau is the dosing interval (24 hr, hence AUC_{0-24}). In addition:

- Trough plasma concentration (C_{trough}) will be measured at the end of the dosing interval (24 hr)
- Minimum plasma concentration (C_{min}) is the lowest concentration during the dosing interval
- Average plasma concentration (C_{av}) is AUC_{0-tau}/tau (i.e. AUC₀₋₂₄/24)
- As a measure of plasma concentration flux, %Peak-trough fluctuation (%PTF)=100%•(C_{max} - C_{trough})/ C_{av} and Swing =100%•(C_{max} - C_{trough})/ C_{trough} will be used

- Time to peak plasma concentration (T_{max}) will be recorded, for both parent and metabolites, although it is expected to be highly variable (variability in T_{max} for extended release drugs at steady-state is recognized.¹³
- As an exploratory metric, and an index of early exposure (potential "dose-dumping"), various partial AUCs from 0-t, and t-24 will be evaluated, with various cutoff times for t (including the population T_{max}, while also recognizing T_{max} as a potential source of error), as recently described by FDA, ^{13,49} and for sustained-release bupropion. ⁵⁰
- Plasma hydroxybupropion AUC₀₋₂₄/bupropion AUC₀₋₂₄ will be used as an index of CYP2B6-mediated bupropion hydroxylation
- Apparent oral bupropion clearance(CL/F) will be determined as dose/AUC
- Metabolite formation clearance (CL_f) will be calculated as the product of the molar fraction of the dose recovered in urine and CL/F.

All results are determined for each subject and each drug product, and reported as arithmetic mean, SD, CV, and geometric mean (and Tmax as the median and range).

Per FDA Guidance, 10 all parameters will be determined for the parent drug released from the dosage form (RS-bupropion). Due to the unusual nature of bupropion (racemate, enantioselective bioactivation, and different pharmacologic effects of the metabolites and their stereoisomers) parameters will also be determined for the major metabolites (hydroxybupropion, erythrohydrobupropion, threohydrobupropion), and for both the individual stereoisomers and the racemate for each analyte.

Additional exploratory analysis may be performed using a population pharmacokinetic approach. In brief, multi-compartmental models will be defined and optimized for bupropion, and then for bupropion and hydroxybupropion simultaneously (and if identifiable, other metabolites). The influence of covariates on the model parameters will be analyzed, where covariates will include age, sex, weight, race/ethnicity, bupropion XL drug product, and *CYP2B6* genotype. Optimal models will be selected based on goodness-of-fit plots, precision of estimates, likelihood ratio test, and evaluation of population predicted estimates, conditional weighted residuals, and relative standard errors of population estimates.

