2.7.3 Statistical Methods

2.7.3.1 Bioequivalence

Bioequivalence will be determined essentially per FDA Guidance, 9,10 using an average bioequivalence approach. A repeated measures model will be fit for each parameter separately. Interpatient variability for each compound will be examined separately prior to assuming that they are all the same. It is anticipated that most parameters will be log-transformed prior to statistical testing, but the distributional assumptions will be examined for each parameter and the most appropriate data transformation used. Following the standard FDA guidance the two one-sided test procedure will be used to determine whether each generic product is significantly less bioavailable than Wellbutrin XL, and whether Wellbutrin XL is significantly less bioavailable than each generic product. This is expressed as a limit of test average/reference average of 80% for the first statistical test and a limit of reference average/test average of 80% for the second statistical test. In practice, the 90% confidence interval around the geometric means of the test/reference ratio for each parameter must be entirely between 0.80 and 1.25 for bioequivalence.

Bioequivalence will be determined using the standard pharmacokinetic parameters (AUC and C_{max}) and equivalence definition (90% CI of the generic/brand geometric mean is within 80-125%) for bupropion (primary), the active metabolite hydroxybupropion (secondary), and for the other metabolites (tertiary). The test for each generic compound will not be adjusted for the other comparisons, e.g. to control the study-wide error rate. Similarly, analysis will not control for multiple comparisons involved in testing each of the parameters. As an aid to interpretation of the results, however, the False Discovery Rate will be computed for the observed results. The generics will also be evaluated using the criteria for bioequivalence for narrow therapeutic index drugs (90% CI of ratio within 0.95-1.05).

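### %PTF and swing are built on the 24 h Ctrough rather than on the separately defined Cmin, so they understate fluctuation and absorb release lag when the minimum falls after dosing

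*Combined protocol and SAP*

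**What the plan says.** Section 2.7.2 gives two different low-concentration measures. For the first: "Trough plasma concentration (C_{trough}) will be measured at the end of the dosing interval (24 hr"). For the second: "Minimum plasma concentration (C_{min}) is the lowest concentration during the dosing interval". The average is AUC over the dosing interval divided by its length. The two measures of concentration flux are then both built on the first: %PTF is the peak minus Ctrough, divided by Cav, and for swing "Swing =100%•(C_{max} - C_{trough})/ C_{trough} will be used". Cmin enters neither formula. The plan gives no reason for this choice, no Cmin-based version and no lag-time parameter.

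Section 2.7.1 lists Cmin, Ctrough, %PTF and swing among the additional pharmacokinetic/bioequivalence endpoints, for bupropion, the metabolites and the individual isomers. Section 2.6.5.1 sets the sampling times: "immediately before and 1, 1.5, 2, 3, 4, 5, 6, 7, 8, 10, 12, 16, 20 and 24 hr after dosing".

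On decision rules, section 2.7.3.1 says that the 90% confidence interval of the test/reference ratio "for each parameter must be entirely between 0.80 and 1.25 for bioequivalence". Its next paragraph says that bioequivalence is determined from AUC and Cmax.

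**The concern.** The 24 h sample is the lowest point of the cycle only if concentrations start to rise as soon as the next dose is taken. These are extended-release tablets inside capsules, taken without washout. If release starts late, the concentration goes on falling after the dose and reaches its minimum during the lag. C24 is then above the minimum, and the longer the lag, the further above it lies. The product with the longer lag therefore looks smoother than it is. Swing is affected more than %PTF because Ctrough is also its denominator.

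What is at stake is how two supportive measures are interpreted. They are the plan's named measures of concentration flux, in a trial that asks about release patterns (section 2.3) and plans to relate patient reports to pharmacokinetic parameters (section 2.7.3.2). With the stated formulas, a difference in swing could reflect fluctuation, lag or both, and a longer lag could partly hide greater fluctuation.

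**Working it through.** The plan gives no numerical value for %PTF or swing, so there is no figure to reproduce. I checked the algebra first and then the size.

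**Algebra.** At steady state with a 24 h interval, a pure lag of L hours replaces C(t) by C(t − L) on a repeating 24 h cycle. Cmax, Cmin and Cav do not change. The 24 h value becomes C(24 − L), which is higher while the curve is still falling. So (Cmax − Cmin)/Cmin and (Cmax − Cmin)/Cav do not depend on L, whereas (Cmax − C24)/C24 and (Cmax − C24)/Cav fall as L grows.

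**Inputs.** From the documents: the formulas and the 15 sampling times. Assumed, because the documents give none: one compartment, first-order absorption rate ka of 0.15 or 0.30/h, half-life 10, 21 or 40 h, and the lag. With k = ln 2/half-life and u the hours since the last release began, in units of bioavailable dose over volume:

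C(u) = ka/(ka − k) × [e^(−k·u)/(1 − e^(−24k)) − e^(−ka·u)/(1 − e^(−24ka))]

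**Worked case: half-life 10 h, ka 0.30/h, lag 0 versus 2 h.** Here k = 0.0693, ka/(ka − k) = 1.3005, 1 − e^(−24k) = 0.8105 and 1 − e^(−24ka) = 0.9993.

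- Cmax, reached at the 5 h sample without lag and the 7 h sample with lag: C(5) = 0.8441 for both.
- Cmin, at 0 or 24 h without lag and at the 2 h sample with lag: 0.3030 for both.
- C24: 0.3030 without lag; C(22) = 0.3474 with lag.
- Cav by the trapezoidal rule on the samples: 0.6011 and 0.6005.
- Plan's swing: 100 × (0.8441 − 0.3030)/0.3030 = 179%, against 100 × (0.8441 − 0.3474)/0.3474 = 143%. Ratio 0.80.
- Plan's %PTF: 100 × 0.5411/0.6011 = 90.0%, against 100 × 0.4967/0.6005 = 82.7%. Ratio 0.92.
- With Cmin, swing is 179% for both and %PTF is 90% for both.

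**Range over the six assumed profiles, at the protocol's sampling times** (ratio of lagged to unlagged product; true fluctuation identical):

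| Lag difference | Swing, plan | %PTF, plan | Swing and %PTF, Cmin |
|---|---|---|---|
| 0.5 h | 0.94-0.96 | 0.95-0.98 | same as plan |
| 1 h | 0.88-0.92 | 0.91-0.96 | 0.99-1.00 |
| 2 h | 0.77-0.85 | 0.83-0.92 | 1.00 |
| 3 h | 0.68-0.77 | 0.74-0.87 | 0.99-1.00 |

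At 0.5 h the Cmin version gives no gain: with no sample between 0 and 1 h, the lowest sampled value is still the one at 0 or 24 h.

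**Sensitivity to the assumed shape.** A second set used half-lives of 8 to 36 h, with ka of 0.25 or 0.5/h or a 6 h zero-order release. On the continuous curve, a 2 h lag gave swing ratios of 0.78-0.87 and %PTF ratios of 0.87-0.95. With Cmin on the protocol's samples the ratios were 0.99-1.00. The exception was zero-order release with a 3 h lag (0.89-0.94), where the sharp peak at 9 h falls between the 8 h and 10 h samples. That is a loss in Cmax, not in Cmin.

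**The case against.** **The decision does not rest on these measures.** A reader might infer from the wording of section 2.7.3.1 that every parameter must meet 0.80-1.25, so that a product could fail bioequivalence on swing through lag alone. The documents do not support this. The same section decides bioequivalence on AUC and Cmax, section 2.7.1 lists %PTF and swing as additional endpoints, and the sample size in section 2.7.4 does not use them. This objection stands.

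**The size is hypothetical.** Nothing in the documents suggests that mean lag differs by 2 h between these products. At 1 h every point ratio lies inside 0.80-1.25. At 2 h only two of six swing ratios are below 0.80 (0.774 and 0.795), and no %PTF ratio is. An interval around a ratio near 0.80 would cross the limit, but that too depends on an assumed lag. This stands as a limit on size, not on direction.

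**A lag difference is real.** A reader might call the resulting difference false. That is too strong: later release is a genuine difference in release pattern, and the plan applies its own definition of trough consistently. The valid criticism is that the measure is not fluctuation alone.

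**Ctrough has something in its favour.** The 24 h sample follows a fasted dose taken in the research unit at a known time. A minimum found before dosing or during a lag still reflects the previous home dose, whose meal conditions are not standardised; section 2.6.5.1 cites food effects of 11% on Cmax and 17% on AUC. This adds noise rather than a bias between products, and rescheduling subjects who are non-adherent in the preceding 7 days limits it. It is a modest cost, and does not justify a fluctuation measure that misses the lowest concentration.

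**Other outputs show the lag.** Cmin, Tmax and partial AUCs are all planned, so a careful reader could notice the lag and recompute. That lowers the stakes, but does not correct the %PTF and swing values the plan would analyse and report.

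**Conclusion.** The point holds for two additional endpoints. Where release is delayed and the minimum falls after dosing, the stated %PTF and swing understate fluctuation and mix release lag into the comparison between products. The direction is exact for a pure lag at steady state. The size depends wholly on assumed lags and kinetics: under the six tabulated profiles, a 1 h difference lowers swing by 8-12% and %PTF by 4-9%, and a 2 h difference by 15-23% and 8-17%. If lags are equal, the ratio between products is not distorted by lag, although fluctuation is understated for each product whenever that lag is above zero. The primary Cmax and AUC0-24 conclusions are untouched. The change is worth making because it is nearly free, not because a main result is at risk.

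**What to change.** In section 2.7.2, define %PTF as 100% × (Cmax − Cmin)/Cav and Swing as 100% × (Cmax − Cmin)/Cmin, with Cmin taken over all samples from 0 to 24 h. Keep Ctrough at 24 h as its own endpoint. Ctrough-based versions can be reported as supportive if wanted.

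The cost is two reworded formulas. No new samples or assays are needed: the samples at 0, 1, 1.5, 2 and 3 h already cover an early post-dose minimum for lags of about 1 h or more. There are two small downsides to state: Cmin may come from a sample that still reflects the previous home dose, and lags shorter than 1 h are not resolved because there is no sample between 0 and 1 h.

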2.7.3 Statistical Methods

2.7.3.1 Bioequivalence

Bioequivalence will be determined essentially per FDA Guidance, 9,10 using an average bioequivalence approach. A repeated measures model will be fit for each parameter separately. Interpatient variability for each compound will be examined separately prior to assuming that they are all the same. It is anticipated that most parameters will be log-transformed prior to statistical testing, but the distributional assumptions will be examined for each parameter and the most appropriate data transformation used. Following the standard FDA guidance the two one-sided test procedure will be used to determine whether each generic product is significantly less bioavailable than Wellbutrin XL, and whether Wellbutrin XL is significantly less bioavailable than each generic product. This is expressed as a limit of test average/reference average of 80% for the first statistical test and a limit of reference average/test average of 80% for the second statistical test. In practice, the 90% confidence interval around the geometric means of the test/reference ratio for each parameter must be entirely between 0.80 and 1.25 for bioequivalence.

Bioequivalence will be determined using the standard pharmacokinetic parameters (AUC and C_{max}) and equivalence definition (90% CI of the generic/brand geometric mean is within 80-125%) for bupropion (primary), the active metabolite hydroxybupropion (secondary), and for the other metabolites (tertiary). The test for each generic compound will not be adjusted for the other comparisons, e.g. to control the study-wide error rate. Similarly, analysis will not control for multiple comparisons involved in testing each of the parameters. As an aid to interpretation of the results, however, the False Discovery Rate will be computed for the observed results. The generics will also be evaluated using the criteria for bioequivalence for narrow therapeutic index drugs (90% CI of ratio within 0.95-1.05).

The influence of *CYP2B6* genetics on the disposition of bupropion, hydroxybupropion, and bioequivalence between brand and generic bupropion XL products will be determined through exploratory analyses to fit individual bioequivalency models by adding random effects for each agent and covariances between the responses. Order effects (omitted in the model described above) will also be determined. Predictors of overall response of each individual for each parameter, CONFIDENTIAL: This document is the intellectual property of [name], PhD. Acceptance of this document constitutes the agreement by the recipient that no unpublished information contained herein will be published or disclosed without prior written approval.

especially CYP2B6 genetics, will be evaluated, specifically the most common variant allele *CYP2B6*6*, comparing *CYP2B6*1/*6* and *CYP2B6*6/*6* genotypes with non-carriers of *CYP2B6*6*, and with true *CYP2B6*1/*1* genotypes.

The influence of stereochemistry on (i) bupropion disposition, (ii) bupropion bioactivation to hydroxybupropion, and (iii) bioequivalence between bupropion XL products will be examined by fitting an expanded model where both the enantiomers and diastereomers will be included by introducing an additional factor, examining the significance of this factor, and its interaction with the specific compound.

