2.1.2 FDA Bioequivalence, Pharmaceutical, Therapeutic, Clinical Equivalence

FDA evaluation of generic drugs uses bioequivalence as a surrogate for therapeutic equivalence, obviating the need for generic drugs to undergo clinical testing. A generic drug is considered bioequivalent to the reference (or branded drug) if the active compound or moiety exhibits the same rate and extent of absorption (more generally, systemic exposure). Systemic exposure is determined from plasma C_{max} and AUC (area under the curve), and the entire 90% confidence interval for the geometric mean of the log-transformed generic-to-reference C_{max} and AUC ratios must be within the bioequivalence limit of 80 to 125%. Generic drugs must also show pharmaceutical equivalence (same active ingredients, route of administration, dosage, form, and strength as the branded drug). Drugs are considered "therapeutic equivalents", without the need for clinical data, if they are both pharmaceutical equivalents and show bioequivalence. While this is reasonable and usually accurate, non-therapeutic equivalence can occur despite bioequivalence, for both

conventional and narrow therapeutic index drugs. ^{12,13} More importantly, it is now clear that single-dose studies in healthy volunteers may not predict steady- state bioequivalence in patients, particularly for modified release forms. ^{13,14}

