2.1.3 Branded and Generic Bupropion

GlaxoSmithKline (GSK) was the innovator of bupropion (Wellbutrin®), first in immediate release (IR) form (TID dosing), then Wellbutrin SR® (sustained release, BID dosing), then Wellbutrin XL® (extended release, once daily dosing). Introduction of generic bupropion IR was followed by generic bupropion SR, then generic bupropion XL.

Approval of the first bupropion XL 300mg generic (Budeprion XL, 2006) was based on a prior bioequivalence study of 150mg Budeprion XL and Wellbutrin XL in healthy subjects, which were then extrapolated to the 300mg product. The pharmacokinetic profile was not expected to differ between 300mg and 150mg bupropion XL; FDA decided not to test bioequivalence of the 300mg products.

Shortly thereafter, FDA received numerous reports of clinical issues when switching from Wellbutrin XL to Budeprion XL. In 2010, FDA sponsored a single-dose crossover bioequivalence study in healthy subjects comparing 300mg Budeprion XL to Wellbutrin XL, completed in August, 2012. ^{15,17} Budeprion XL failed bioequivalence testing. Based on these results, Budeprion XL 300mg was withdrawn from the market in October, 2012. In fact, none of the currently available 300mg XL generics has undergone bioequivalence or clinical equivalence testing.

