2.7.4 Sample Size Justification

Calculations for sample size and power of the proposed studies are based on information from the confidence intervals for the ratio of the pharmacokinetic parameters for the generic (Budeprion XL) to the innovator (Wellbutrin XL) which was recently reported by the FDA in their evaluation of Budeprion XL.⁵¹

SAS 9.3's Proc Power was used to conduct the correct power analysis for the two one-sided tests (TOST) approach per the FDA guidance on bioequivalence. Using a 90% confidence interval and ratios needing to be between 0.80 and 1.25, the power for sample sizes ranging from a conservative estimate of 60 to the recruitment goal of 75 was computed. If the comparators are indeed bioequivalent (ratio=1.0) then the study power would be >0.999 for a pharmacokinetic parameter such as AUC and 0.98 for a more variable parameter such as C_{max} . If the generic is 10% under (or over), e.g. ratio=0.90,

then for AUC the power would be 0.78=0.83 to declare a significant difference between the compounds at an alpha of .05 even if the CI for the ration was still contained within the 0.80-1.25 bounds.

Ver 1.02

The study is also powered in order to have a reasonable power of detecting clinical differences between compounds. If one of the generics is non-equivalent with respect to symptom and it is assumed that 25% suffer a relapse on this generic versus 5% for Wellbutrin or other (equivalent) forms, then using a McNemar's test for equality of proportions, a sample size of 60 and a 1-tailed alpha of 0.05, the power will be about 0.83. For continuous variables, there will be 0.80 power to detect a standardized difference of 0.37 (low-medium effect size).

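### Does the supplementary 0.95-1.05 check need to be dropped or re-specified because the trial has almost no power to meet it?

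*Combined protocol and SAP*

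**What the plan says.** Section 2.7.3.1 sets average bioequivalence with two one-sided tests. A generic is bioequivalent if the 90% confidence interval for the geometric mean ratio lies wholly between 0.80 and 1.25. Bupropion is primary, hydroxybupropion secondary and the other metabolites tertiary. The section ends: "The generics will also be evaluated using the criteria for bioequivalence for narrow therapeutic index drugs (90% CI of ratio within 0.95-1.05"). It does not say which analytes or metrics this covers, or how a pass or a failure is to be read.

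Section 2.7.4 gives power for 60 to 75 subjects, "Using a 90% confidence interval and ratios needing to be between 0.80 and 1.25". At a true ratio of 1.0 the stated power is above 0.999 for AUC and 0.98 for the more variable Cmax. A further figure supposes a true ratio of 0.90 and concerns a test of difference: "for AUC the power would be 0.78=0.83 to declare a significant difference between the compounds at an alpha of .05". The equals sign in it evidently stands for a range. Power for 0.95-1.05 is not mentioned. Section 2.7.4 takes its variability from the FDA evaluation of Budeprion XL and prints no SD or CV.

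**The concern.** A prespecified pass/fail criterion normally comes with some idea of how likely a truly equivalent product is to pass. Here there is none, and the plan's own power figures suggest the chance is close to zero for parent bupropion. If all three generics miss 0.95-1.05, the bare result says little, because identical products would be expected to miss it too. The trial compares named marketed generics with the brand after an earlier generic was withdrawn, so a statement that every generic failed the narrow limits could be misread as evidence of a real difference.

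**Working it through.** **Inputs.** From section 2.7.4: n = 60 to 75; power 0.78 to 0.83 for an AUC difference at ratio 0.90 and alpha 0.05; equivalence power above 0.999 (AUC) and 0.98 (Cmax) at ratio 1.0 within 0.80-1.25. From section 2.7.3.1: "90% CI of ratio within 0.95-1.05".

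**Model.** Paired log ratio with SE = SD/√n and df = n − 1. Half-width of the 90% CI = t(0.95, df) × SE. Pass probability is exact two-one-sided-tests power on the log scale. The limits are ln 0.95 = −0.0513 and ln 1.05 = 0.0488, so a perfectly centred interval needs a half-width below 0.0488.

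**Step 1: the plan's own figures.** Without a printed SD they cannot be computed forward, only checked for consistency. I solve two-sided difference power at ln 0.90 = −0.1054:
- 0.78 at n = 60 gives SD 0.294 (SE 0.294/√60 = 0.0379).
- 0.83 at n = 75 gives SD 0.309 (SE 0.309/√75 = 0.0357).

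SD 0.294 at n = 60 gives equivalence power 0.99997 within 0.80-1.25, which agrees with the stated value above 0.999. One SD does not reproduce both ends exactly: 0.294 gives difference power 0.865, not 0.83, at n = 75.

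For Cmax, the power of 0.98 is stated at ratio 1.0. It gives SD 0.430 (n = 60) or 0.482 (n = 75).

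**Step 2: expected interval at an observed ratio of exactly 1.00.**
- AUC, SD 0.294, n = 60: 1.671 × 0.0379 = 0.063, interval 0.939-1.065.
- AUC, SD 0.294, n = 75: half-width 0.057, interval 0.945-1.058.
- Cmax, either SD at its own n: half-width 0.093, interval 0.911-1.097.

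All are already wider than 0.95-1.05.

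**Step 3: chance that an identical product passes 0.95-1.05.**

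| Metric and SD | n = 60 | n = 75 |
|---|---|---|
| AUC, 0.294 | 0.04% | 0.41% |
| AUC, 0.309 | 0.009% | 0.11% |
| AUC, 0.249 (most favourable: 0.83 at n = 60, true ratio 1.10) | 1.7% | 8.2% |
| AUC, 0.20 (assumed, CV about 14%) | 22% | 38% |
| Cmax, 0.430 | below 1e-8 | below 1e-8 |

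A pooled four-period error term with more degrees of freedom lowers the AUC figures at the inferred SDs further. An 80% chance would need an SD of 0.131 (n = 60) or 0.147 (n = 75). At the inferred SDs it would need about 298 subjects for AUC (SD 0.294) and 636-798 for Cmax.

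**Step 4: can the check mislead in the other direction?** At a true ratio of 0.95 and SD 0.294, the pass probability is 0.02% (n = 60) or 0.14% (n = 75). The check cannot plausibly produce a false claim of tight equivalence. Its only error is failing products that are the same.

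**Step 5: what depends on it.** The word *also* in the sentence makes the check additional. The same section ties bioequivalence to 0.80-1.25. Each ratio and its 90% CI are computed for that decision anyway, and comparing the same interval with a second pair of limits changes neither estimate nor interval.

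**The case for a change.** The strongest case for a change is that a pass/fail rule should not be prespecified when failure is nearly certain whether the product is identical or 5% different. Even at the assumed SD of 0.20, identical products would still fail on AUC 62-78% of the time (100% minus 38% and 22%). Labelling the check descriptive and printing the SD would take one sentence and two numbers.

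The arithmetic stands, and so does the point that a bare fail label carries little information. Three things limit it.

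- The interval is more than the label. An interval lying wholly outside 0.95-1.05 would be informative whatever the power, and a pass would be strong evidence.
- The SD is inferred. Section 2.1.3 describes the FDA work as a study where "FDA sponsored a single-dose crossover bioequivalence study in healthy subjects comparing 300mg Budeprion XL to Wellbutrin XL", and section 2.1.2 warns that "single-dose studies in healthy volunteers may not predict" steady-state bioequivalence in patients. If that study supplied the variability, steady-state variability could differ in either direction, and this trial will measure it.
- Nothing is known here about metabolite variability. The sentence is not limited to parent drug, so deleting it would remove the check for analytes on which there is no evidence against it.

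**Conclusion.** No change to the plan is needed. On the inferred variability, identical products would meet 0.95-1.05 on AUC about 0.01-0.4% of the time with 60-75 subjects (about 8% at most on the readings tried), and essentially never on Cmax. That is a true description of a strict supplementary benchmark. It is not a fault in the design: the plan promises no power for it, the decision rule is 0.80-1.25, and the check can only err towards withholding a tighter claim. Dropping it would exchange a conservative extra for brevity and leave every reported ratio and interval as it is. The missing interpretation is a gap that analysts fill sensibly by showing the interval beside both sets of limits and noting that missing the narrower one is not evidence of non-equivalence. The figures rest on a paired analysis, a two-sided difference test, the 0.78-0.83 range belonging to n = 60-75, and the stated powers referring to parent bupropion. Nothing is claimed for metabolites.
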